9.1.4 Peripheral Blood Analysis

9.1.4.1 Plasma: Plasma samples will be stored at [name] for batched analysis. Plasma will be interrogated for chemokine and cytokine levels using a multiplex platform from Eve Technologies (<https://www.evetechologies.com>).

9.1.4.2 Cryopreserved samples: Cryopreserved samples will be stored [name] for batched analysis. Samples will be thawed and stained with fluorophore-conjugated antibodies against one or more of the following: CD4, CD8, CD25, CD62L, CD45RA, CD127, ICOS, PD-1, PD-L1, FoxP3, CD3, CD56, CD16, CD83, TIM-3, Ki-67, CD19, CD20, CD33, CD15, CD11b, HLA-DR and others. Stained cells will be interrogated by flow cytometry and results analyzed using FlowJo or similar software.

9.1.4.3 RNAlater samples: Cells in RNA later will be stored [name] for batched analysis. Samples will be thawed and RNA will be extracted. The transcriptome will be analyzed by RNA deep sequencing (RNAseq) using the Illumina HiSeq platform. Targeted RT-PCR will be used to validate genes of interest identified by RNAseq. TCR deep sequencing data may also be obtained from the RNAseq.

9.1.5 The evaluating pathologist will assess the percentage of the surgical specimen that contains live tumor.

- 9.1.6 Sections will be subject to immunohistochemical evaluation of the marker Ki-67 pre- and post-operatively to estimate the tumor cell population capable of proliferation after treatment (68). Since the monoclonal antibody Ki-67 detects a nuclear antigen expressed in all phases of the cell cycle except G0, this offers a unique means to assess response to radiotherapy. This approach has never before possible with standard breast radiation treatment, because standardly treatment is delivered after all measurable tumor has been removed.

9.2 Gene Expression Profiling and Advanced Imaging:

- 9.2.1 RNA will be procured using the Tissue Bank quality control measures fixed paraffin embedded tissues pre-radiation (from biopsy) and post-radiation (surgical specimen).
- 9.2.2 We will perform global gene expression profiling using RNAseq to identify differential expression patterns that correlate with response to radiation. We will utilize the MCW Human and Molecular Genetics Center Sequencing Core to perform RNAseq and analysis. Total RNA will be extracted using Trizol per the MCW Tissue Bank's standard procedure, and the total RNA will be poly-A purified, transcribed, and chemically fragmented using Illumina's TruSeq RNA library kit. Libraries will be prepared for each sample, indexed for multiplexing, and then sequenced on an Illumina HiSeq 2000. Briefly, we will plan to multiplex 4 libraries per lane x 8 lanes per flow cell, enabling us to test 32 samples per flowcell, a setup which has routinely yielded us 150-180 million reads (87.5% mapped reads) per lane. For data analysis, sequencing reads will be demultiplexed and compressed into FASTQ files using CASAVA 1.8 or equivalent software, aligned to the human genome by TopHat (69), and analyzed for transcript abundance using Cufflinks (70). Cufflinks produces FPKM (fragments per Kb of exon per million fragments mapped) values for all transcript isoforms. The CuffDiff2 program (part of Cufflinks package) then statistically analyzes differences in transcript abundance, taking into account variance between biological replicates and correction for false discovery rate (71).
- 9.2.3 Expression of genes from patients with pathologic complete response versus non-complete responders will be compared using an unpaired t test on all probes, with a false-discovery rate (FDR) of less than 0.05. If <15% complete pathologic responses are seen, then partial responses versus no response will be compared.
- 9.2.4 Expression of genes from patients with pre- and post-radiation will be compared, with a false-discovery rate (FDR) of less than 0.05.
- 9.2.5 Gene expression data from this patient group will be compared to previously published gene expression signatures for radiation sensitivity, and OncotypeDx, a metric that predicts chemotherapy response (79,89,90).
- 9.2.6 Correlation of MR parameters and gene expression differences will be performed as described previously (90). Correlation of MRI parameters and CT-imaging with pathologic responses will also be determined.
- 9.2.7 Additional focus will be placed on genes with a statistically significant change in expression (with $p < 0.05$). Pathway analysis will be used to identify likely putative genes which modulate radiation response. Targets identified as potentially leading to enhanced responsiveness will be used to generate a novel gene signature and tested and validated as prognostic factors in future studies.

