9.0 Pathologic Evaluation and Genetic Evaluation of Tissue Specimens

9.1 Pathological Evaluation and Immune Biomarkers

- 9.1.1 The surgical specimens will be subject to routine pathological analysis. Remaining tissue from the pre-treatment biopsy, as well as any residual tumor tissue post-RT, will be stored in accordance with MCW department of Pathology guidelines. Routine hematoxyline and eosin (H&E) stain will be used for morphological analysis and for the determination of immune cell infiltrates. The samples will be assessed by the breast pathologist as previously described (65,66). One H&E slide and 20 unstained slides will be reserved for Gene Expression Profiling (described in section 9.2 below).
- 9.1.2 Immune cell infiltrates have previously been shown to correlate with both breast cancer-specific outcomes and response to neoadjuvant treatment (67). We anticipate that enhanced immune cell infiltration (determined as described above in 8.1.1, or with additional immunostains if needed and tissue available allows) will correlate with pathologic responses to RT.
- 9.1.3 Blood specimens (50mL, collected in 10mL lavender top EDTA tubes) will be obtained at the time of routine blood draws: once pre- and once post-radiation, (last day and up to one week after +/- 1 treatment) for future studies of immune markers/peripheral blood cells and other cancer and treatment related biomarkers that will attempt to predict radiation side effects and potentially treatment responses. These samples will be obtained at Froedtert Hospital, and in order to spare patient additional travel, those receiving radiation treatment outside Froedtert may opt out of the blood draw at the end of radiation. These samples will also be stored on the MCW Campus and analysis will be performed on campus. The process for handling specimens will be as follows:
 - 9.1.3.1 After collection, invert tube(s) multiple times to ensure adequate mixing of EDTA. ***Call the co-PI's laboratory ([name]) at [contact] to let them know they need to come pick up the PBMCs. If no answer, call the co-PI at [contact]. The plasma will be processed in the laboratory performing the blood draw, and the PBMCs will be collected by the PI's laboratory member for the remainder of the processing outlined below.**

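### Tumor RNA is taken from fixed paraffin-embedded tissue, but section 9.2.2 prescribes a sequencing workflow for intact RNA, and specimen type coincides with time point in the pre/post comparison

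*Combined protocol and SAP*

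**What the plan says.** Objective 2.2.8 includes measuring how tumor gene expression changes with radiation and relating that to pathologic response. The material and methods are set out in sections 9.1 and 9.2 and partly repeated in 11.3.

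- **Source.** Section 9.2.1 names "fixed paraffin embedded tissues pre-radiation (from biopsy) and post-radiation (surgical specimen" as the source. Section 9.1.1 adds: "One H&E slide and 20 unstained slides will be reserved for Gene Expression Profiling". The fixative itself is not named.
- **Quality control.** Section 9.2.1 states: "RNA will be procured using the Tissue Bank quality control measures". No metric, threshold or rule for a failed sample follows.
- **Extraction and library.** Section 9.2.2 states: "Total RNA will be extracted using Trizol per the MCW Tissue Bank's standard procedure", and then "the total RNA will be poly-A purified, transcribed, and chemically fragmented", with a TruSeq RNA kit. Cufflinks is to give values for every transcript isoform, and CuffDiff2 is to test differences.
- **Throughput.** The plan is to "multiplex 4 libraries per lane x 8 lanes per flow cell, enabling us to test 32 samples per flowcell", a set-up said to have "routinely yielded us 150-180 million reads (87.5% mapped reads) per lane".
- **Comparisons.** Section 9.2.3 compares complete with non-complete responders by an unpaired t test. Section 9.2.4 compares pre- with post-radiation expression. Both use a false-discovery rate below 0.05. Section 9.2.7 carries genes with p < 0.05 into pathway analysis and on to a new signature.

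No frozen or RNAlater-preserved tumor tissue is planned. RNAlater is specified only for blood cells (9.1.3.7 and 9.1.3.9).

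**The concern.** Two adjacent items do not fit each other. Poly-A purification captures a molecule by its 3' tail. If the RNA is whole, the entire transcript is recovered. If it is already broken, only the piece carrying the tail is kept and the rest is lost. A further chemical fragmentation step then shortens what remains, and isoform estimates need reads along the whole transcript. With fixed, embedded tissue the likely results are libraries that fail and libraries weighted to the 3' end.

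The statistical problem comes from how the samples are arranged. In 9.2.4 time point and specimen type are the same variable. If biopsy and resection blocks yield RNA of different quality, that difference enters the contrast in full and is read as a response to radiation. Section 9.2.7 would carry such genes into a candidate signature, and section 1.7 wants the translational work to serve as a baseline for later studies.

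**Working it through.** The question is mainly whether the stated method suits the stated material. The arithmetic only fixes its extent.

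**1. The plan's own figure.** Four libraries per lane x 8 lanes = 32 samples per flow cell, as 9.2.2 says. Reads per library: 150/4 = 37.5 million to 180/4 = 45.0 million. At 87.5% mapped this is 32.8 to 39.4 million. The plan does not say what type of input RNA gave this yield, so it is no evidence about paraffin tissue.

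**2. Extent.** Section 11.1 enrols 40 patients. With two specimens each, 40 x 2 = 80 tumor libraries. This is an upper limit, because 9.1.1 stores post-radiation tumor only where some remains, so a complete responder may have no second library.

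**3. Source against method.**

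| Step | What the plan specifies | Fit with fixed paraffin tissue |
|---|---|---|
| Source (9.2.1) | Paraffin-embedded biopsy and resection | RNA generally fragmented (assumption) |
| Extraction (9.2.2) | Trizol, by the tissue bank's procedure | Nothing specific to paraffin stated |
| Selection (9.2.2) | Poly-A purification | Keeps mainly 3' pieces of broken RNA |
| Fragmentation (9.2.2) | Chemical | Shortens RNA that is already short |
| Quantification (9.2.2, 11.3) | Isoform level | Needs coverage along the transcript |
| Quality limit | None stated | Poor libraries may enter unnoticed |

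**4. Confounding in 9.2.4.** Pre = biopsy and post = resection for every patient. The expected pre/post difference for a gene is therefore (radiation effect) + (specimen-type effect), and no subset of the samples separates the two terms.

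**5. Why false-discovery-rate control does not help.** It limits findings due to chance. A technical shift is a real difference between the two sets of measurements. As an illustration, assume 40 complete pairs, no biological change, and a technical shift of d standard deviations of the paired difference. A two-sided paired t test at 0.05 then has noncentrality d x √40 on 39 degrees of freedom:

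| Assumed d | Chance that one gene reaches p < 0.05 |
|---|---|
| 0 | 5% |
| 0.25 | 34% |
| 0.50 | 87% |
| 0.75 | 99.6% |

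The values of d are assumptions, and 9.2.4 does not name a paired t test. The table shows the mechanism and does not estimate what will happen in this trial.

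**The case against.** **The harm is not documented.** No section reports that this workflow fails on these blocks, and no fixation times or RNA-quality data are given. This stands, so the point is worded as a risk. It rests on the general fact that fixed, embedded RNA is fragmented and on how poly-A capture works.

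**Quality is delegated.** Both procurement and extraction refer to tissue-bank procedures that a reader cannot see. This is a real but partial safeguard. It would be wrong to infer that quality control is absent. However, no metric or limit is stated, and a pass/fail check would not remove a systematic difference between biopsies and resections.

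**The size is easily overstated.** A reader might infer that thousands of genes will look radiation-responsive, or that a set share of pairs will be lost. The documents give no shift and no failure rate, so neither can be supported. Nor do they show that fixation differs between specimens. Block age differs by the gap between biopsy and surgery, which the protocol's windows hold to about 90 + 60 + 18 + 56 = 224 days, but storage time before extraction is not given.

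**The reach is limited.** A reader might infer that all of objective 2.2.8 depends on these libraries. Its immune part also draws on stained infiltrates, plasma cytokines, flow cytometry and RNAlater-preserved blood cells, none of which pass through this workflow. The confounding belongs to 9.2.4 only, since 9.2.3 does not say that it contrasts specimen types. Gene expression is also not among the secondary endpoints listed in 11.2.

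**Bench detail is not a protocol fault.** At 32 per flow cell, 80/32 = 2.5, so three flow cells are needed. How pairs are placed on them can be left to the sequencing core.

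**Conclusion.** The mismatch between 9.2.1 and 9.2.2 holds on the protocol's own text, and no other section resolves it. Following 9.2.2 as written risks failed or 3'-biased libraries among at most 80 tumor samples. In 9.2.4 any quality difference between biopsy and resection is inseparable from a radiation effect.

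The conclusion assumes that RNA in these blocks is fragmented, as is general for fixed tissue, and that the unseen tissue-bank procedures do not already replace the stated steps. The size of any bias cannot be derived from the documents. The effect is confined to the tumor-expression part of objective 2.2.8 and the analyses that use it. The primary endpoint, the two-stage design and its error rates, and the blood RNA sequencing are unaffected. The change is worth making before tissue is processed, because it is cheap then and the slides reserved are limited.

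**What to change.** In 9.2.2, with matching text in 11.3:

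1. Replace the Trizol, poly-A and chemical-fragmentation steps with an extraction method made for fixed tissue and a ribosomal-RNA-depleted or exome-capture library.
2. State one RNA-fragment-size quality limit, apply it to biopsy and resection alike, and say what happens to samples that fail it.
3. State that the expression comparisons are run at gene level. Sections 9.2.3 and 9.2.4 already speak of genes, so this mainly removes the dependence on isoform estimates.
4. Report RNA quality by specimen type, and add a quality-adjusted sensitivity analysis of 9.2.4 using a model that accepts a covariate. Say plainly that it cannot fully separate specimen type from time. The unpaired t test in 9.2.3 takes no covariate, so the adjustment belongs to 9.2.4.

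The cost is a different kit, some loss of isoform detail, and one further analysis. No extra tissue, procedure or visit is needed.

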10.0 Patient Assessments

10.1 Study Parameters

- 10.1.1 See Appendix 1 for a summary of assessments and time frames
- 10.1.2 Breast assessments will be conducted during radiation therapy with one ideally occurring on the last day of treatment
- 10.1.3 A breast exam must be conducted by a Physician, Physician Assistant or Nurse Practitioner at clinic visits and documented 42 days prior to study entry, 4-6 weeks post radiation, prior to surgery, no later than one month after the last surgery (post-operative visit), six months after surgery, 12 months after surgery (+/- 2 months) and then annually until 5 years after treatment is completed. The annual follow-up interval of 12 months +/-2 months will be calculated from the actual date of the last follow-up visit.
- 10.1.4 Post-operative complications (the primary endpoint of the study) will be defined as any complication occurring within 3 months of surgery. These may include but are not limited to: post-operative infection requiring oral/IV antibiotics (CTCAE grade 2 or higher), need for hospital re-admission due to surgical complications, wound dehiscence (CTCAE grade 2 or higher), significant hematoma at the operative site requiring drainage (CTCAE grade 2 or higher), and persistent symptomatic seroma formation that will be defined as need for seroma drainage or need for pain medications because of seroma formation (CTCAE grade 2 or 3), or any need for re-operation excluding re-excision for concerns related to resection margin.
- 10.1.5 At follow-up visits (see Appendix I for schedule), documentation will be made of disease status (no evidence of disease, local recurrence, regional recurrence, or distant recurrence) and toxicity. Toxicity will be graded according to CTCAE v4.0.

10.2 Cosmetic Outcomes

- 10.2.1 Physician reported cosmetic outcome has been consistently reported from prospective studies evaluating new methods for breast radiation. It is important to document physician reported cosmetic outcomes with this novel treatment method as well.
- 10.2.2 Physician assessed cosmetic outcome will be assessed prior to radiation, at the end of radiation, one month following radiation prior to surgery, one month after the last surgery, six months after surgery, 12 months after surgery and then annually until 5 years after treatment is completed.
- 10.2.3 Cosmetic assessments will be assessed using a 4 point scale. The form contained in Appendix III will be used for data collection.
- 10.2.4 Digital photographs will be taken of the treated and untreated breasts using an RTOG established protocol familiar to the research associates at Froedtert Hospital. These images will be taken prior to treatment, one month after surgery, then 6 months, 12 months, 24 months and 36 months after surgery. Two digital images will be taken at each of these assessment points. One will be a close up of the treated breast alone in order to provide detailed information regarding the treatment effects. The second digital image will be a straight frontal view of both breasts taken in either a standing or seated position with the patient's hands symmetrically placed on her hips. Care will be taken to exclude the face and framing and focusing will be done to include both the treated and untreated breast to allow optimal comparison for symmetry.
- 10.2.5 Photos will then be saved in MCW's secure I: drive with the following naming convention:

Save photo as: "Case #, View, Time Point" (ex. 7 Single_6mo; or 12 Both_1)

Breast View: Single = Treated breast; Both = Both breasts

Time Point: B=Baseline prior to radiation; 1mo = 1 month post-surgery; 6mo = 6months post-surgery; 1 = 1 year post-surgery; 2 = 2 years post- surgery; 3 = 3 years post-surgery

- 10.2.6 The digital images will later be evaluated for cosmetic results by the investigators using the criteria established in previous trials (again see Appendix III). It is of interest and important to obtain multiple measures of cosmetic outcome. With this protocol, three methods will be undertaken – physician reported outcomes assessed at time of follow-up, photographs to be evaluated by the investigators, and patient reported outcomes as described in the next section.
- 10.3 Quality of Life Outcomes and Patient Reported Outcomes
- 10.3.1 The Breast Cancer Treatment Outcome Scale (BCTOS) is a 22 item measure of perceived aesthetic (e.g. breast shape) and functional status (e.g. pain and mobility) that has been used after breast conserving therapy and radiation (Appendix IV)
- 10.3.2 The BCTOS has high reliability and validity and has been used in a variety of previous studies on recovery from breast cancer treatment, including studies of post-operative APBI.
- 10.3.3 The BCTOS focuses on symptoms that are specifically relevant to radiation therapy (e.g. skin problems, breast tenderness, fibrosis)
- 10.3.4 These forms will be completed prior to treatment, at the end of treatment, one month after radiation, one month after surgery, then 6 months after surgery, then 12 months, 24 months, 36 months, 48 months and 60 months after surgery or chemotherapy (if given), whichever is later. These may be collected +/- 2 months from the specified time points.
- 10.3.5 The BCTOS will ideally be completed at clinic visits, but may be completed by mail or over the phone by research associates.
- 10.3.6 As the BCTOS has been used on previous studies of radiation therapy, the data collected from this study can then be compared to historical controls of patients treated with more traditional post-operative radiation therapy regimens including post-operative APBI.
- 10.4 Patient Safety Monitoring and Confidentiality
- 10.4.1 This study will be reviewed by the Medical College of Wisconsin Cancer Center Data and Safety Monitoring Committee (MCWCC DSMC). A summary of the MCWCC DSMC activities are as follows:
- 10.4.1.1 Review the clinical trial for data integrity and safety
 - 10.4.1.2 Review all unexpected grade 3, and all grade 4, and 5 adverse events, as well as any others requiring expedited reporting as defined in this protocol. (Grades 4 & 5 events must be reported to the DSMC within 5 calendar days of study staff's knowledge.)
 - 10.4.1.3 Review all Data and Safety Monitoring reports.
 - 10.4.1.4 Submit a summary of any recommendations related to study content.
 - 10.4.1.5 Terminate the study if deemed unsafe for patients.
- 10.4.2 A copy of the MCWCC Data and Safety Monitoring Plan and membership roster will be maintained in the study research file and updated as membership changes. The committee will review reports from the study PI twice annually (or more

frequently if needed) and provide recommendations on trial continuation, suspension or termination as necessary.

10.4.3 Any available DSMC letters will be submitted to the IRB of record as required.

10.4.4 Data on patient information and follow-up information will be collected and entered into the password protected OnCore system. Data will be accessible only by the research team and DSMC.

10.4.5 Hard copy forms (see Appendix III and IV) will be kept in a locked file in offices of the CTO. The forms will be linked to patients by a unique identifier and patient initials in the event that the identifier is transcribed incorrectly. Access to these forms will be limited to the CRA and PI only as the data collected will be entered in to OnCore.

11.0 Statistical Considerations

11.1 Sample Size, Power Calculations, and Comparison of Post-Operative Complications to Historical Controls

The primary endpoint of this study will be post-operative complications (as defined in section 10.1.4). The complication rate measured on this study will be compared to a historical control of 32% of patients, as outlined in section 1.6. This will be measured on an individual patient level. Hence a surgical complication rate that exceeds 31% will be considered unacceptable and result in a negative study. A post-op complication rate of 14% or less will be considered a successful demonstration of the safety of this treatment. This number was selected because it is roughly half the complication rate observed on the study by Horton et.al. (94) and represents an increase in complication rate of only 8% over that reported by Boostrom et.al. (102). To demonstrate this, a Simon's two stage design (104) will be used for this study. The value of this approach is that in stage 1 it can be demonstrated that pre-operative APBI using this dose and fractionation scheme is not excessively risky. Once that condition is satisfied, stage 2 is then used to demonstrate that it meets a better standard of complications compared to the Horton study with only a modest increase in complications when compared with historical series of complications observed without pre-operative radiation therapy.

For this analysis we assume as a null hypothesis that the true complication rate is 0.31. This will be tested against a one-sided alternative. In stage one of accrual, 17 patients will be enrolled. If there are 5 or more complications in these 17 patients, enrollment will be suspended and the study will be evaluated for possible closure. This will serve as the stopping rules for the study under the null hypothesis of a 31% complication rate. Otherwise, 22 additional patients will be accrued (total 39) in stage two, and the null hypothesis will be rejected if there are 7 or fewer complications among the 39 total. This design yields a type I error rate of approximately 0.05 and power of 0.80 when the true complication rate is 14%. With this design, the probability of stopping early is 0.6453. To allow for possible withdrawal prior start of treatment or other unforeseen problem with enrollment, total enrollment will be 40 patients.

Sample size for Simon's Two-Stage Design was calculated using a web-based calculator (retrieved February 11, 2016) (106).

In 2012-2013, 586 new cases of invasive breast cancer were seen at FH. This included 424 patients who had stage I and IIA disease, the population targeted in this proposal. We estimate that 60-70% of these patients would be eligible for screening, with 30-40% eligible for the study. This will allow for an adequate pool of patients for the targeted enrollment of 40 patients.

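### Section 11.1 says stage 2 will demonstrate a small excess of complications over surgery alone, but rejecting the null supports only a true rate below 31%

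*Combined protocol and SAP*

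**What the plan says.** **Interpretive text, section 11.1.** The primary endpoint is introduced with "The complication rate measured on this study will be compared to a historical control of 32% of patients". Two labels follow: "Hence a surgical complication rate that exceeds 31% will be considered unacceptable and result in a negative study" and "A post-op complication rate of 14% or less will be considered a successful demonstration of the safety of this treatment". The 14% is justified as roughly half the rate in the earlier pre-operative single-fraction study, and because it "represents an increase in complication rate of only 8% over that reported by" a surgical series, whose figure is 6%. Stage 2 is then described as demonstrating a better standard than the earlier pre-operative study, "with only a modest increase in complications when compared with historical series of complications observed without pre-operative radiation therapy".

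**Formal design, section 11.1.** The null is a true complication rate of 0.31 with a one-sided alternative. With 5 or more complications among the first 17 patients, "enrollment will be suspended and the study will be evaluated for possible closure". Otherwise 22 more are accrued and "the null hypothesis will be rejected if there are 7 or fewer complications among the 39 total". The stated properties are a type I error of about 0.05, "power of 0.80 when the true complication rate is 14" per cent, and an early-stopping probability of 0.6453.

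**Sources and endpoint.** Section 1.6 gives the 32% as seroma formation in the earlier pre-operative study, and the 6% as clinically significant seroma in a series of 167 breast-conserving operations. It also gives infection rates of 1% to 5% after surgery without pre-operative radiation. Section 10.1.4 defines the endpoint as any complication within three months of surgery, including infection, readmission, dehiscence, haematoma, symptomatic seroma and re-operation. Section 11.2 plans exact confidence intervals for re-excision and response. No interval is named for the primary endpoint.

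**The concern.** The text promises two conclusions and the design tests one. Neither 6% nor 14% has a hypothesis, margin or confidence bound. The 14% enters the design only as the rate at which power is 0.80, and the 6% only as part of the reason for choosing 14%. A trial ending with 7 of 39 would be formally positive and, on the text as written, could be reported as having shown a small excess over surgery alone, or a rate of 14% or less.

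This bears on the trial's main message. Section 2.1 makes demonstration of safety the primary objective, and section 1.7 says that meeting the safety endpoints could make the regimen a template for later studies.

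A smaller point is that the two label sentences follow one about the measured rate and do not say that they mean true rates. Someone writing the report could apply 14% to the observed proportion.

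**Working it through.** **Inputs (section 11.1).** Stage 1: 17 patients, continue with 4 or fewer complications. Stage 2: 22 more, reject with 7 or fewer of 39. Null 0.31, design alternative 0.14.

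**1. The plan's own figures.** For a final limit of s complications and true rate p,

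R(s, p) = Σ (x = 0 to 4) P(Bin(17, p) = x) × P(Bin(22, p) ≤ s − x).

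- At p = 0.31, s = 7, the five terms are 0.0012 + 0.0063 + 0.0139 + 0.0158 + 0.0099 = 0.0471 (type I error).
- At p = 0.14, s = 7, R = 0.8050 (power).
- Early stopping under the null: P(Bin(17, 0.31) ≥ 5) = 0.6453.

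All three agree with the plan.

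**2. Chance of a positive result at other true rates, R(7, p).**

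| True rate | P(reject 31%) | Points above 6% |
|---|---|---|
| 14% | 0.805 | 8 |
| 18% | 0.569 | 12 |
| 20% | 0.444 | 14 |
| 24% | 0.233 | 18 |
| 31% | 0.047 | 25 |

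Rejecting 31% when the truth is 20% is a correct rejection. It shows only that a positive trial is compatible with rates well above 14%.

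**3. What the boundary result shows.** 7/39 = 17.9%.

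- Ordinary exact (Clopper-Pearson) two-sided 95% interval: 7.5% to 33.5%.
- Two-stage 90% interval, ordering results by stage reached and then by number of complications. The upper limit solves R(7, p) = 0.05, giving 30.8%. The lower limit solves 1 − R(6, p) = 0.05, giving 8.6%.
- Ordinary one-sided 95% upper limit: 31.1%. This is just above the null that the test rejects, so the two-stage interval is the one consistent with the decision rule.

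Both two-sided intervals extend far above 14%.

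**4. If 14% were applied to the observed rate.** 5/39 = 12.8% and 6/39 = 15.4%, so success would need 5 or fewer. With the same stage 1 rule, R(5, 0.31) = 0.008 and R(5, 0.14) = 0.53. The stated 0.05 and 0.80 belong only to the limit of 7.

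**5. The reference figures.** The 6% and the 32% are both seroma rates, while the endpoint counts any complication. If the seroma and infection rates of section 1.6 are added for surgery alone, on the assumption that no patient has both, the range is 6 + 1 = 7% to 6 + 5 = 11%. That is still narrower than the endpoint.

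**The case against.** The strongest reply is that 31% and 14% are the ordinary unacceptable and desirable rates of a Simon design. Section 11.1 moves straight from the 14% rationale to the two-stage design, and its next paragraph calls both figures true rates. That is the better reading, and it stands. A reader might infer that the section sets two conflicting decision rules and leaves 6–7 of 39 or 8–12 of 39 without a verdict. The documents do not support that: the formal rule classifies every result of a study that passes stage 1 and completes stage 2. What remains is a request to say plainly that the two rates are true rates.

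A second reply is that the main clause of the stage 2 sentence concerns the earlier pre-operative study, that section 1.6 openly expects complications to exceed those of surgery alone, and that no margin is attached to the word modest. This is fair, and it rules out treating 8 points as a margin the trial had to exclude. A 95% upper limit at or below 14% is not a reasonable demand when the truth is 14%: any valid limit achieves that at most 5% of the time, whatever the sample size. But an increase with no margin and no test is not something a trial demonstrates.

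A third reply is that 6% is too narrow a benchmark to measure an excess from. This also stands. Against the 7% to 11% range, the boundary intervals (7.5% to 33.5% and 8.6% to 30.8%) include the upper part. It would therefore be wrong to infer that a result of 7/39 proves a large excess over surgery alone. It shows neither a large excess nor a small one.

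**Conclusion.** The stated conclusion goes beyond the test. A positive result supports a true complication rate below 31% and nothing tighter, and the chance of such a result is still 0.44 at a true 20%. The formal design is correct, and its error rate, power and early-stopping probability reproduce. A reader might conclude that the design is miscalibrated or that the decision rule contradicts itself; neither follows.

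The weight is minor to moderate: no boundary or sample size is at fault, but the headline claim of the trial is. The figures assume independent patients with a common complication rate, 39 evaluable patients, and no continuation after 5 or more complications in stage 1. The finding that nothing is tested against 6% or 14% needs no assumption; it is read directly from section 11.1.

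**What to change.** In section 11.1:

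- State that 31% is the true rate under the null and 14% the true rate under the design alternative, and that neither is a cut-off for the observed rate.
- State that a study that passes stage 1 and completes stage 2 is positive only with 7 or fewer of 39 patients having a complication, and that rejection supports only a true rate below 31%.
- Replace the promised demonstration against surgery alone with a descriptive comparison to the figures in section 1.6 (6% seroma, 1% to 5% infection), noting that the endpoint is broader than either and that the 32% is also a seroma figure.
- Report the observed rate with a confidence interval that follows the two-stage design, for example the 90% interval used above.

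The cost is one added interval, and the plan gives up the claim to demonstrate a small excess over surgery alone. Sample size, boundaries, the stage 1 rule, type I error and power do not change.
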